### **HCV Genotype/Subtype**

Phylogenetic analysis will be conducted on HCV NS3/4A and/or NS5A sequence from baseline samples from all subjects in order to accurately determine genotype/subtype. If the phylogenetic analysis is not available, then the result from Sanger sequencing of a region of NS5B by AbbVie or by the Central laboratory will be used to determine the subject's HCV genotype/subtype, if available. Finally, if neither the phylogenetic analysis result nor the Sanger sequencing assay results is available, then the Inno-LiPA assay results from the Central laboratory will be used to categorize the subject. This information will be presented in summaries of efficacy subgroup analyses.

The baseline characteristic summary will use the results from the central laboratory (Sanger sequencing or Inno-LiPA 2.0 Assay [if Sanger sequencing not available]). A summary of HCV genotype subtype as provided by the central laboratory (Sanger sequencing or Inno-LiPA 2.0 Assay [if Sanger sequencing not available]) versus phylogenetic analysis also will be provided. Listing of HCV genotype and subtype will be provided separately for central laboratory results and phylogenetic analysis results.

### 10.8.1 Presence of Baseline Polymorphisms for Subgroup Analyses of SVR12

For the efficacy subgroup analyses defined in Section 10.6, any NS3/4A variant and any NS5A variant are defined as follows using the subset of signature amino acid positions of interest for HCV (Table 9), where baseline variants based on  $\geq 15\%$  NGS detection threshold are considered.

For example, all HCV genotype 2 subjects with any baseline variant at amino acid positions 155, 156, or 168 will be counted as having any NS3/4A variant at baseline; any HCV genotype 2 subjects with any baseline variant at amino acid positions 24, 28, 30, 92, or 93 will be counted as having any NS5A variant at baseline.

**Table 9. Amino Acid Positions for Subgroup Analysis**

Target	Genotype	Subgroup Amino Acid Positions (All Variants at These Positions are to Be Included)
NS3/4A	1, 2, 3, 4, 5, 6	155, 156, 168
NS5A	1a	28, 30, 31, 93, H58D, E62A
	1b	31, 93
	2	24, 28, 30, 92, 93
	3	24, 28, 30, 31, 58, 93
	4	24, 28, 30, 31, 93
	5	24, 28, 30, 31, 58, 92, 93
	6	24, 28, 30, 31, 58, 92, 93

The number and percentage of subjects in the ITT and mITT-VF populations will be summarized for the presence of baseline resistance- associated variants of:

1. Any NS3/4A variant at baseline (yes/no);
2. Any NS5A variant at baseline (yes/no);
3. Any NS3/4A variant at baseline **or** any NS5A variant at baseline (yes/no);
4. Both NS3/4A and NS5A variant at baseline (i.e., any NS3/4A variant at baseline and any NS5A variant at baseline) (yes/no);
5. Presence or absence of any variant
  - 5a. Any NS3/4A variant at baseline only (i.e., without baseline NS5A variants);
  - 5b. Any NS5A variant at baseline only (i.e., without baseline NS3/4A variants);
  - 5c. Both NS3/4A and NS5A variant at baseline;
  - 5d. None (i.e., no baseline variant in either NS3/4A or in NS5A at baseline).

## **10.9 Patient Reported Outcomes**

The Kidney Disease Quality of Life (KDQOL36™) instruments will be used to collect patient reported outcomes (PROs). The KDQOL-36 is a disease specific Quality of Life instrument to be used in patients with chronic kidney disease. The KDQOL-36 consists of 4 subscales aimed at quantifying both general health and disease specific attributes. The subscales include: the Short Form-12 (a general health subscale SF-12), burden of kidney disease, symptoms/problems, and effects of kidney disease. The results of the SF-12 instrument are summarized into the Physical Component Summary (PCS) score and the Mental Component Summary (MCS) score. The raw scores are transformed linearly to a range of 0 to 100, with higher scores indicating better health-related Quality of Life.

Summary statistics for each protocol-specified visit (number of non-missing observations, mean) and for change from baseline to each protocol-specified, post-baseline visit

(number of non-missing observations, mean, standard deviation, minimum, maximum) will be provided for the KDQOL-36 subscale scores (SF-12 summarized by PCS and MCS, burden of kidney disease, symptoms/problems, and effects of kidney disease).

If a subject starts another treatment for HCV, then all PRO values for this subject measured on or after the start date of the new HCV treatment will be excluded from analyses.

## **11.0 Safety Analysis**

### **11.1 General Considerations**

Safety analyses will be performed using the safety population. Data will be summarized overall (across all arms).

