### **4.0 Study Objectives, Design and Procedures**

#### **4.1 Objectives**

The primary objectives of this study are to assess the efficacy (by evaluating the percentage of subjects achieving SVR12) and safety of GLE/PIB in adults with chronic hepatitis C virus (HCV) genotype (GT) 1 – 6 infection with compensated cirrhosis or without cirrhosis and with chronic renal impairment in both HCV TN and TE subjects. The efficacy of GLE/PIB will be assessed based on the overall population (i.e., across treatment durations, genotypes, and cirrhosis status), and the safety of GLE/PIB will be assessed by treatment duration and cirrhosis status across genotypes.

The secondary objectives are to assess the efficacy of GLE/PIB based on the overall population (i.e., across treatment durations, genotypes, and cirrhosis status) by evaluating the following:

- The percentage of subjects with HCV on-treatment virologic failure;
- The percentage of subjects with HCV virologic relapse.

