### **5.1.3 Safety Population**

All subjects who receive at least one dose of study drug will be included in the safety population. Safety analysis will be performed on the overall ITT population, combining Arms A, B and C.

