### **9.1 Exposure**

The duration of exposure to study drug will be summarized for each treatment arm and overall in the safety population. Duration of exposure is defined for each subject as the last study drug dose date minus the first study drug dose date plus 1 day.

During each treatment period, descriptive statistics (mean, standard deviation, median, minimum, and maximum) will be presented for exposure. Study drug duration will also be summarized with frequencies and percentages using the following categories:

- 1 to 15 days
- 16 to 30 days
- 31 to 45 days
- 46 to 60 days
- 61 to 75 days

- 76 to 90 days
- 91 to 105 days
- > 105 days

In addition, the number and percentage of subjects with study drug duration of  $\geq 52$  days for Arm A,  $\geq 77$  days for Arm B and  $\geq 103$  days for Arm C will be summarized.

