### **Adverse Event Overview**

An overview of AEs will be presented, consisting of the number and percentage of subjects experiencing at least one event for each of the following AE categories:

- Any treatment-emergent AE;
- Treatment-emergent AEs with a "reasonable possibility" of being related to DAAs (glecaprevir/pibrentasvir);
- Treatment-emergent AEs of grade 3 or higher;
- Treatment-emergent AEs of grade 3 or higher with a "reasonable possibility" of being related to DAAs (glecaprevir/pibrentasvir);
- Serious treatment-emergent AEs;
- Serious treatment-emergent AEs with a "reasonable possibility" of being related to DAAs (glecaprevir/pibrentasvir);
- Treatment-emergent AEs leading to discontinuation of study drug;
- DAA-related treatment-emergent AEs leading to discontinuation of study drug;
- Serious treatment-emergent AEs leading to discontinuation of study drug;
- Treatment-emergent AEs leading to interruption of study drug;
- Treatment-emergent AEs leading to death;
- Deaths.

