### **Adverse Events by SOC and PT**

The following summaries of AEs by SOC and PT will be generated by treatment arm and overall:

- Treatment-emergent AEs;
- Treatment-emergent AEs with a "reasonable possibility" of being related to DAAs (glecaprevir/pibrentasvir);
- Treatment-emergent AEs of grade 3 or higher;
- Treatment-emergent adverse events of grade 3 or higher with a "reasonable possibility" of being related to DAA (glecaprevir/pibrentasvir);
- Serious treatment-emergent AEs;
- Serious treatment-emergent AEs with a "reasonable possibility" of being related to DAAs (glecaprevir/pibrentasvir);
- Treatment-emergent AEs leading to discontinuation of study drug;
- DAA-related treatment-emergent AEs leading to discontinuation of study drug;
- Serious treatment-emergent AEs leading to discontinuation of study drug;
- Treatment-emergent AEs leading to interruption of study drug;
- Treatment-emergent AEs leading to death.

A listing of treatment-emergent AEs grouped by SOC and preferred term with subject numbers will be created.

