changing in CKD stage (improvement, no change, or decline) between screening and EOT will also be summarized and graphed by treatment arm. For CKD 3B and 4 subjects at screening, a listing will be provided for subjects with CKD stage worsening based on any eGFR criteria or initiated dialysis treatment during the treatment and post treatment period. A separate listing will also be provided for subjects not on dialysis prior to screening while started dialysis post screening.

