### **11.5 Analysis of Child-Pugh Score**

For subjects with compensated cirrhosis, Child-Pugh scores will be categorized as 5, 6, > 6, or missing at baseline and each protocol-specified post-baseline visit, including applicable post-treatment visits. Shift tables from baseline to each post-baseline visit will be created for the cirrhotic subjects in the safety population. The shift tables will cross-tabulate the frequency of subjects with baseline values in each category versus the post-baseline categories. For each baseline category and across the baseline categories, the percentage of subjects in each post-baseline category (excluding the post-baseline category of missing) will be calculated.

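### Sections 5.1.3 and 11.1 pool all arms for safety, contradicting the Section 4.1 objective (by duration and cirrhosis status) and the by-arm tables in 11.2.2; the objective is only partly answered

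*SAP*

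**What the plan says.** Section 4.1 treats efficacy and safety differently within the primary objectives. Efficacy is to be judged on the whole population, whereas "the safety of GLE/PIB will be assessed by treatment duration and cirrhosis status across genotypes".

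The safety sections set a different rule. Section 5.1.3: "Safety analysis will be performed on the overall ITT population, combining Arms A, B and C". Section 11.1: "Data will be summarized overall (across all arms").

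Some individual outputs depart from that rule:

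- Section 11.2.2, SOC and preferred term tables: "The following summaries of AEs by SOC and PT will be generated by treatment arm and overall".
- Section 11.3.2, change in CKD stage: "between screening and EOT will also be summarized and graphed by treatment arm".
- Section 9.1, exposure: "The duration of exposure to study drug will be summarized for each treatment arm and overall in the safety population".
- Section 11.5, Child-Pugh score, restricted to one cirrhosis stratum: "Shift tables from baseline to each post-baseline visit will be created for the cirrhotic subjects in the safety population".

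Other outputs name no grouping. The adverse event overview is an example: "An overview of AEs will be presented, consisting of the number and percentage of subjects experiencing at least one event".

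**The concern.** Sections 4.1, 5.1.3, 11.1 and 11.2.2 cannot all be followed. A programmer who applies Section 11.1 wherever no grouping is named will produce overall-only tables for most laboratory, hepatic and vital-sign outputs, although the objective asks for duration and cirrhosis status. Cirrhosis status is an SVR12 subgroup in Section 10.6, where the objective is the overall population. It is not a grouping variable for adverse events, laboratory values or vital signs, where the objective names it.

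Two things are at stake. A hepatic signal confined to subjects with cirrhosis would be averaged over a population in which they are at most about a quarter. And if the grouping is left unsettled, it may be chosen after data from an open-label study have been seen.

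**Working it through.** **The plan's own figure.** The only precision figure in the SAP is the SVR12 half-width in Section 4.3: 1.96 × √(0.97 × 0.03 / 120) = 0.0305, stated as 0.031. It reproduces and does not bear on this point. The rest is mainly a comparison of sections.

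**What arm tells us (Section 4.2).**

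| Arm | Duration | Cirrhosis |
|---|---|---|
| A | 8 weeks | none |
| B | 12 weeks | all (compensated) |
| C | 16 weeks | mixed (all treatment-experienced GT3) |

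A by-arm table therefore gives duration completely. It gives cirrhosis status exactly in Arms A and B, but not in Arm C.

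**What each safety output specifies.**

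| Output | Section | By arm? | By cirrhosis status? |
|---|---|---|---|
| Exposure | 9.1 | yes | no |
| Eleven SOC/PT summaries | 11.2.2 | yes | no |
| CKD stage change | 11.3.2 | yes | no |
| Child-Pugh shifts | 11.5 | not stated | subjects with cirrhosis only |
| Adverse event overview | 11.2.2 | not stated | no |
| PT-only, severity and relationship tables | 11.2.2 | not stated | no |
| Hepatic decompensation events | 11.2.3 | not stated | no |
| Laboratory changes, shifts and grades | 11.3.2 | not stated | no |
| Hepatic laboratory criteria | 11.3.2 | not stated | no |
| Vital signs | 11.4.2 | not stated | no |

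Where the table says not stated, the overall rule in Section 11.1 governs.

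**How far pooling could mask a difference.** The inputs from Section 4.2 are about 120 subjects in total and up to about 30 with cirrhosis. The event rates and counts are assumptions, because the SAP gives none, and the cap is assumed to be filled.

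- Assumed rates of 20% in 30 subjects with cirrhosis and 5% in 90 without: (0.20 × 30 + 0.05 × 90) / 120 = 10.5 / 120 = 8.75%. The pooled table shows one figure and hides a 15-point difference.
- Extreme case, three events, all in subjects with cirrhosis: 3/30 = 10% (Wilson 95% CI 3.5% to 25.6%), shown as 3/120 = 2.5% (0.9% to 7.1%). The ratio of four is 120/30, the most that pooling can dilute a rate at these sizes.

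**Precision of the split.** At an assumed 10% rate, the Wilson 95% interval is 5.8% to 16.7% for 12/120 and 3.5% to 25.6% for 3/30. The estimate for subjects with cirrhosis is imprecise but usable as description.

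**Risk windows.** Section 11.2.1 counts events up to 30 days after the last dose. The nominal windows are 56 + 30 = 86, 84 + 30 = 114 and 112 + 30 = 142 days. A pooled adverse event percentage mixes these; the by-arm SOC/PT tables do not.

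**The case against.** A reader might infer that all safety data are pooled and the safety objective is not answered at all. The SAP does not support that:

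- Section 11.2.2 gives eleven adverse event summaries by arm, including serious, grade 3 or higher, drug-related, discontinuation and fatal events.
- The first eleven lines of the adverse event overview are the same eleven categories. Subjects are counted once in the overall total, so those lines can be read by arm from the SOC/PT tables. Only the line for all deaths has no by-arm counterpart.
- Exposure, CKD stage change and, in Section 8.1, reasons for discontinuing study drug are by arm.
- Child-Pugh shifts are shown for subjects with cirrhosis.

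A reader might also take the four-fold dilution as the expected effect. It is a constructed maximum, with every event in one stratum and the cirrhosis cap filled. Subjects meeting the hepatic laboratory criteria, and those with hepatic decompensation events, are also listed individually, so a few cases would not be lost from view.

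Section 5.1.3 can further be read as defining a population, and Section 11.1 as a default that specific sections override. The study is descriptive with no hypothesis test, so no error rate or power is affected.

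All of this stands, and it limits the point. It does not remove it. On the default reading, every output with no named grouping is still overall only, and that includes the hepatic outputs where cirrhosis status matters most. The SAP does not say that the listings show cirrhosis status, and a listing is not a summary by group. Nothing in Section 11 separates Arm C by cirrhosis status for adverse events, laboratory values or vital signs.

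**Conclusion.** The plan contradicts itself. The overall-only rule in Sections 5.1.3 and 11.1 conflicts with the objective in Section 4.1 and with the by-arm tables in Section 11.2.2. As written, the objective is answered for adverse events by duration, and by cirrhosis status in Arms A and B. It is not answered by cirrhosis status in Arm C. For the hepatic decompensation events, laboratory changes, shifts and grades, hepatic laboratory criteria and vital signs, it is answered on neither factor. The gap in the overview is small, because most of its lines can be recovered.

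The size of any masking depends on event rates and on the number of subjects with cirrhosis, neither of which is known. The SAP gives no expected size for Arm C, so the number whose cirrhosis status the by-arm tables leave unresolved cannot be stated. The conclusion rests on the text and not on the illustrations. It is worth correcting before database lock because it concerns a stated primary objective, but no efficacy result depends on it.

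**What to change.** State the grouping once, in Sections 5.1.3 and 11.1: safety is summarized overall, by treatment arm (duration) and by cirrhosis status, with each Arm C subject allocated by the status recorded in IRT/EDC (Section 7.1). Apply it to the outputs in Sections 11.2.2 and 11.2.3, to the laboratory and hepatic summaries in Section 11.3.2, and to vital signs in Section 11.4.2, so that these agree with Section 4.1.

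To limit duplication with Arms A and B, count tables could instead use the columns Arm A, Arm B, Arm C without cirrhosis, Arm C with cirrhosis, and overall. Counts by duration and by cirrhosis status both follow from these by addition.

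The cost is SAP wording and extra table columns; arm and cirrhosis status are already collected. Estimates for the group with cirrhosis (up to about 30 subjects) will be imprecise and should be presented as descriptive. Sample size and efficacy analyses do not change.

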### **11.2 Analysis of Adverse Events**

Adverse events (AEs) will be coded using the Medical Dictionary for Regulatory Activities (MedDRA). The actual version of the MedDRA coding dictionary will be noted in the clinical study report.

#### **11.2.1 Treatment-Emergent Adverse Events**

Treatment-emergent AEs are defined as any AE with an onset date that is after the first dose of study drug and no more than 30 days after the last dose of study drug. Events where the onset date is the same as the study drug start date are assumed to be treatment-emergent. If an incomplete onset date was collected for an AE, the event will be assumed to be treatment-emergent, unless there is other evidence that confirms that the event was not treatment-emergent (e.g., the event end date was prior to the study drug start date).

#### **11.2.2 Tabulations of Treatment-Emergent Adverse Events**

The number and percentage of subjects with treatment-emergent AEs will be tabulated by primary MedDRA System Organ Class (SOC) and preferred term (PT). The SOCs will

be presented in alphabetical order, and the preferred terms will be presented in alphabetical order within each SOC.

Subjects reporting more than one AE for a given PT will be counted only once for that term (most severe/highest grade incident for the severity tables and most related incident for the relationship tables). Subjects reporting more than one AE within a SOC will be counted only once for that SOC. Subjects reporting more than one AE will be counted only once in the overall total.

### **Adverse Event Overview**

An overview of AEs will be presented, consisting of the number and percentage of subjects experiencing at least one event for each of the following AE categories:

- Any treatment-emergent AE;
- Treatment-emergent AEs with a "reasonable possibility" of being related to DAAs (glecaprevir/pibrentasvir);
- Treatment-emergent AEs of grade 3 or higher;
- Treatment-emergent AEs of grade 3 or higher with a "reasonable possibility" of being related to DAAs (glecaprevir/pibrentasvir);
- Serious treatment-emergent AEs;
- Serious treatment-emergent AEs with a "reasonable possibility" of being related to DAAs (glecaprevir/pibrentasvir);
- Treatment-emergent AEs leading to discontinuation of study drug;
- DAA-related treatment-emergent AEs leading to discontinuation of study drug;
- Serious treatment-emergent AEs leading to discontinuation of study drug;
- Treatment-emergent AEs leading to interruption of study drug;
- Treatment-emergent AEs leading to death;
- Deaths.

### **Adverse Events by SOC and PT**

The following summaries of AEs by SOC and PT will be generated by treatment arm and overall:

- Treatment-emergent AEs;
- Treatment-emergent AEs with a "reasonable possibility" of being related to DAAs (glecaprevir/pibrentasvir);
- Treatment-emergent AEs of grade 3 or higher;
- Treatment-emergent adverse events of grade 3 or higher with a "reasonable possibility" of being related to DAA (glecaprevir/pibrentasvir);
- Serious treatment-emergent AEs;
- Serious treatment-emergent AEs with a "reasonable possibility" of being related to DAAs (glecaprevir/pibrentasvir);
- Treatment-emergent AEs leading to discontinuation of study drug;
- DAA-related treatment-emergent AEs leading to discontinuation of study drug;
- Serious treatment-emergent AEs leading to discontinuation of study drug;
- Treatment-emergent AEs leading to interruption of study drug;
- Treatment-emergent AEs leading to death.

A listing of treatment-emergent AEs grouped by SOC and preferred term with subject numbers will be created.

### **Adverse Events by PT**

The number and percentage of subjects experiencing treatment-emergent AEs will be tabulated according to PT and sorted by overall frequency in the safety population. Similar summaries will be provided for grade 3 or higher treatment emergent AEs, DAA-related treatment-emergent AEs, DAA-related grade 3 or higher treatment-emergent AEs, and DAA-related treatment-emergent serious AEs.

### **Adverse Events by Maximum Severity Grade Level**

Treatment-emergent AEs and DAA-related treatment-emergent AEs will be summarized by maximum severity grade level of each preferred term. Each AE will be assigned a grade level (grade 1, 2, 3, 4, or 5) by the investigator. If a subject has an AE with unknown severity, then the subject will be counted in the severity grade level category of "unknown," even if the subject has another occurrence of the same event with a severity present. The only exception is if the subject has another occurrence of the same AE with the highest grade level (grade 5). In this case, the subject will be counted under the "Grade 5" category.

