### **Adverse Events by Maximum Relationship**

Treatment-emergent AEs also will be summarized by maximum relationship of each preferred term to study drug (DAAs), as assessed by the investigator. If a subject has an AE with unknown relationship, then the subject will be counted in the relationship category of "unknown," even if the subject has another occurrence of the same event with a relationship present. The only exception is if the subject has another occurrence of the same AE with a relationship assessment of "Reasonable Possibility." In this case, the subject will be counted under the "Reasonable Possibility" category.

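### In the maximum-severity AE tables, a known Grade 3 or 4 event is shown as 'unknown' when the same subject also has an ungraded occurrence of that preferred term

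*SAP*

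**What the plan says.** SAP Section 11.2.2 opens with a general counting rule. A subject with several AEs under one preferred term is counted once, at the "most severe/highest grade incident for the severity tables and most related incident for the relationship tables".

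Under the subheading on maximum severity grade, all treatment-emergent AEs and the DAA-related ones "will be summarized by maximum severity grade level of each preferred term". The same paragraph says "Each AE will be assigned a grade level (grade 1, 2, 3, 4, or 5) by the investigator". It then provides for a missing grade: the subject is placed in an 'unknown' category "even if the subject has another occurrence of the same event with a severity present". One exception follows: "The only exception is if the subject has another occurrence of the same AE with the highest grade level (grade 5"), in which case the subject is shown as Grade 5.

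Separate severe-event counts are planned elsewhere in Section 11.2.2. The AE overview has a line for "Treatment-emergent AEs of grade 3 or higher", the tables by SOC and preferred term include the same category, and for the tables by preferred term alone, "Similar summaries will be provided for grade 3 or higher treatment emergent AEs". DAA-related versions are planned in all three places. None of these states a rule for unknown grades.

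**The concern.** If one occurrence of a term is Grade 3 and another is ungraded, the true maximum is at least Grade 3. That lower bound is certain, yet the maximum-severity table discards it and shows the subject exactly as it would show one with no grade at all.

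Two consequences follow. First, the Grade 3 and 4 rows can only lose known events through this rule, never gain them. Second, the grade 3 or higher summaries count subjects with at least one qualifying event, so they keep the same subject. For one preferred term, the Grade 3 to 5 rows of one table may then not add up to the grade 3 or higher count in another.

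The study is non-comparative and plans about 120 subjects, so severe events under a given term will often be read one by one. It helps if the table that displays grade shows every severe grade on record.

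**Working it through.** The SAP attaches no figure to this rule, so there is nothing to reproduce. The check applies the two counting rules to the same subject and then scales the result.

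**Inputs**
- Rule A, from the maximum-severity paragraph: any ungraded occurrence gives 'unknown', unless another occurrence of the term is Grade 5.
- Rule B, from the opening of Section 11.2.2: count the highest grade. Applied to known grades, this leaves 'unknown' only where no occurrence is graded.
- Planned size: about 120 subjects (SAP Sections 4.2 and 4.3).

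**Step 1. One subject, one preferred term**

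| Occurrences of the term | Rule A | Rule B | Has a known event of grade 3 or higher? |
|---|---|---|---|
| ungraded + Grade 1 | unknown | Grade 1 | no |
| ungraded + Grade 2 | unknown | Grade 2 | no |
| ungraded + Grade 3 | unknown | Grade 3 | yes |
| ungraded + Grade 4 | unknown | Grade 4 | yes |
| ungraded + Grade 5 | Grade 5 | Grade 5 | yes |
| ungraded only | unknown | unknown | no |

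The rules differ in four of the five mixed cases. In two of those four, Grades 3 and 4, the subject also belongs in the grade 3 or higher summaries, so the tables disagree.

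**Step 2. Size of the disagreement**

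For one preferred term, let n3, n4 and n5 be the subjects in the Grade 3, 4 and 5 rows under Rule A, U those under 'unknown', and S the count in the grade 3 or higher summary. Let k be the subjects with a known Grade 3 or 4 occurrence, an ungraded occurrence and no Grade 5. Then

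S − (n3 + n4 + n5) = k, with 0 ≤ k ≤ U.

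The gap is bounded by the 'unknown' count. A reader with both tables can find k by subtraction, but cannot tell from them how k splits between Grade 3 and Grade 4.

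**Step 3. Scale**

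Each affected subject moves 1/120 = 0.0083, about 0.83 percentage points, from a graded row to 'unknown' for that term. The SAP gives no expected number of ungraded AEs. By way of illustration only, k = 0, 1 or 2 within one term gives 0, 0.83 or 1.67 points (2/120).

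**The case against.** The strongest defence is that the rule is deliberate and coherent. The table reports a maximum, and the maximum of a known and an unknown grade is undetermined unless the known one is already at the ceiling. Grade 5 is the ceiling, hence the only exception. The relationship tables follow the same pattern: 'unknown' yields only to the top category, a reasonable possibility of relatedness. On this reading the general highest-grade rule is silent on missing grades, and the later paragraph supplies the special case. A programmer would know which to apply.

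Much of this stands. The rule is a convention for missing data rather than a slip, and the departure from the general rule is an exception stated in the same section. Showing an ungraded plus Grade 1 subject as Grade 1 would assert a maximum that nobody knows. Ungraded AEs should also be rare, because the investigator is to grade every AE and Section 4.4 calls for data cleaning before lock. Zero affected subjects is a realistic outcome.

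A reader might go further than the text allows and infer that recorded severe events vanish from the safety report. They do not: the subject remains visible under 'unknown' in the same table, and the event still counts in the overview, the SOC and preferred-term tables, and the preferred-term tables for grade 3 or higher. Nor does the SAP support a forecast of a shift of several points in any row, since it gives no rate of missing grades and several affected subjects would have to share one preferred term.

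The defence does not show that hiding a known Grade 3 or 4 gains anything. Doubt about whether the true maximum is higher justifies a flag on the subject. It does not require withholding a grade already established as a minimum.

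**Conclusion.** The point holds in a limited form. Followed as written, the maximum-severity tables place a subject with a known Grade 3 or 4 occurrence and an ungraded occurrence of the same term under 'unknown'. The Grade 3 and 4 rows then understate known severe events and do not agree with the grade 3 or higher summaries.

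Severity is low. The effect touches only these descriptive tables (all treatment-emergent AEs and the DAA-related ones), occurs only if a grade is still missing at analysis, and amounts to about 0.83 points in one row per affected subject. That figure assumes the planned 120 subjects as denominator. The conclusion also assumes that the grade 3 or higher summaries are programmed as written, with no unstated override for unknown grades. No efficacy result is affected.

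**What to change.** Widen the exception in the maximum-severity paragraph. Suggested wording: *A subject with an occurrence of unknown severity and another occurrence of the same preferred term of known Grade 3, 4 or 5 will be counted at the highest known grade. Subjects counted in this way at Grade 3 or 4 will be identified in a footnote or listing, because their true maximum may be higher.*

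For a known Grade 1 or 2 with an ungraded occurrence, two choices are acceptable: keep 'unknown', or show the known grade with the same footnote. The SAP should state which.

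The cost is about one sentence of SAP text, a small programming change, and a footnote or short listing. The small downside is that the displayed grade is a lower bound for the footnoted subjects. In return, the Grade 3 to 5 rows agree with the grade 3 or higher count for each preferred term.
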